# **5.3** Evaluations

Will you perform any laboratory tests for this study?

🗹 Yes 🛛 No

If **Yes**, describe the following:

- List all laboratory tests to be done as part of the study (e.g., hematology, clinical chemistry, urinalysis, pregnancy testing).
   CBC without differential, urine pregnancy test, HbA1c, Lipid profile, Basic metabolic panel, Liver panel, TSH, urine urea nitrogen. The OGTT will be performed to measure insulin sensitivity and beta cell response.
- Differentiate screening laboratory test(s) from those taken after enrollment.
  - List special assays or procedures required to determine study eligibility or assess the effect of the intervention (e.g., immunology assays, pharmacokinetic studies, images, flow cytometry assays, microarray, DNA sequencing). For research laboratory assays, include specific assays, estimated volume and type of specimen needed for each test. For procedures, provide special instructions or precautions. The above are the screening laboratory tests. If the subject has diabetes, hypertension, hyperthyroidism etc. she will be ruled out based on exclusion criteria. The special assays listed above are NA
- Include specific test components and estimated volume and type of specimens needed for each test. The initial visit will obtain a total of ~91cc (baseline eligibility labs plus OGTT). Subsequent visits will obtain ~83cc only for the OGTT component of the study. When there is lack of funding, subsequent pre-pregnancy visits will only obtain ~49cc of blood for the OGTT and pregnancy metabolic visits will obtain ~25cc for a fasting blood sample. Blood collection procedures may revert to those previously-approved if additional funding is secured.
- Specify laboratory methods to provide for appropriate longitudinal and cross-sectional comparison (e.g., use of consistent laboratory method throughout study, use of single, central laboratory for multi-site studies).

The glucose from the OGTTs will be obtained real-time onsite or in the MIRI lab. The estimated intra-assay coefficient of variation is  $\sim 2\%$ . The rest of the laboratory studies will be batched so that each subject's complete analysis is obtained at one time. The intra-assay coefficient of variation varies depending on the test but is generally less than 5% and the inter-assay coefficient of variation is generally less than 10%.

• If more than one laboratory will be used to perform study tests, specify which evaluations will be done by each laboratory.

The Tufts Medical Center and Brigham & Women's Hospital labs will perform the routine laboratory studies at the 3-month postpartum metabolic visit. A urine pregnancy test as a POC test will be performed before each metabolic visit, except the pregnancy visits; additionally, a urine pregnancy POC test will be performed by LIPP staff when a  $VO_{2max}$  test is done outside of the metabolic visit. The glucose and cytokine measures will be performed in the Maternal Infant Research Institute (MIRI) and BWH Research Facility, and the insulin and enteroinsular axis response will performed at the Pennington Biomedical Research Institute.

- Specify if the laboratory tests that will be performed are in compliance with Clinical Laboratory Improvement Amendments (CLIA) of 1988. If not, explain why.
   All laboratory tests performed in the TMC and BWH hospital laboratories will be performed in compliance with Clinical Laboratory Improvement Amendments (CLIA) of 1988. The studies performed in the MIRI and PBRC will be performed for research purposes only.
- If samples will be stored for the purpose of this study, describe the preparation, handling, and storage of specimens, including specific time requirements for processing, required temperatures, Page 26 of 54

# aliquots of specimens, where they will be stored, how they will be labeled, and what will happen to the samples after the study is over (e.g. will be destroyed).

Samples from CTRC or the HNRCA will be placed on ice and then brought to the MIRI during the 3 hour OGTT or fasting blood draw, or processed on site. Samples will be aliquoted in separate vials in the MIRI to avoid freeze thaw cycles. Samples will be bar coded using a unique identifier code for subject name and study visit. Samples not run real time, will be stored in -80°Cfreezers in the MIRI. Samples not used at the completion of the study will be destroyed. The cord blood samples at the time of delivery will be brought to the MIRI for processing (glucose), and then aliquots stored at -80°C for analysis of insulin, cytokines and lipids. Samples from the BWH Research Facility will be handled in a similar manner but in the BWH research lab.

The placentas obtained at the time of delivery will be fixed for histological analysis, submerged in RNA Later, or snap frozen in liquid nitrogen and stored at -80°C for molecular analysis. For a subset of the subjects, we will obtain fresh placental tissue for lipid metabolism activity assays.

After participants have completed the study, insulin, c-peptide, and incretin samples will be sent to the PBRC site for analysis. Similarly, inflammatory markers, other biomarkers as noted and placental samples, will be shipped to TMC or BWH for analysis. An MTA will be obtained from the respective sites prior to shipping.

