Specific Aim 2: To determine the molecular effects whereby lifestyle intervention initiated before pregnancy can improve placental mitochondrial lipid oxidation and accumulation. The working hypothesis is that lifestyle intervention before pregnancy will increase placental mitochondrial lipid oxidation and decrease lipid esterification/storage (Fig. 2). Isotope-

labeled fatty acid oxidation and esterification will be quantified in vitro in placental explants. We will measure markers of mitochondrial lipid metabolism and content using qRT-PCR and ELISA approaches. Placental lipids will be quantified and correlated with neonatal adiposity and maternal metabolism.

Impact of the study: Clinically, the proposal provides feasible methods to improve short and longterm metabolic health of obese women and their offspring. Scientifically, this study will provide fundamental insights into the physiological and molecular mechanisms underlying maternal pregravid metabolism and effects on maternal/placental physiology.

Specify which are the primary or secondary aims or objectives of this study as applicable. The primary objective is the main question. Secondary objectives are goals that will provide further information for the study

We have not developed secondary aims for the study. These will be considered once the primary study is underway and secondary funding is sought. For example, we are in preliminary discussions with [name] in the school of nutrition to look at any spillover effect of the LIPP study on other family members. These discussions are at the initial stages and have not yet been fully developed or sought additional research funds.

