covariate-adjusted difference of 146 g fat mass between groups. We have 80% power to detect an absolute or covariate-adjusted difference as small as 126 g fat mass between groups. Corresponding 95% CI for the absolute or covariate-adjusted difference in neonatal fat mass between groups will be reported. For secondary analyses, we will be using the same

statistical approach. Based on our preliminary data, we estimate the SD of birth weight to be 700 g; with 50 neonates in each group we will have 90% power to detect an absolute or covariate-adjusted difference of 455 g in birth weight and 80% power to detect a 393g difference between groups. Additional secondary analyses will include umbilical cord cytokines. Comparisons will be performed using a two-sample t-test at a significance level of  $\alpha$ =0.05; however, Mann-Whitney U tests or log transformations will be employed if data are not normally distributed. Linear regression models, including confounding factors, will be used to perform covariate adjustments. Based on our published data (80), we estimate the standard deviations of umbilical cord IL-6 and CRP to be 3.4 pg/ml and 7,900 ng/ml, respectively. With 50 women in each group, we will have 90% power to detect an improvement in IL-6 and CRP levels of 50% and 42%, and 80% power to detect an improvement of 42% and 36%, respectively.

The primary goal of Aim 2 is to determine the effect of lifestyle intervention prior to pregnancy on placental mitochondrial fatty acid oxidation at term. We hypothesize that placental  $\beta$ -oxidation will be higher in the LIPP group. We will conduct an intent-to-treat analysis using two sample t-test or non-parametric Wilcoxon rank-sum test to assess differences between groups. Regression analysis will be used to assess the association of placental  $\beta$ -oxidation and enzyme activity with maternal inflammatory cytokine levels and insulin resistance in early pregnancy, along with neonatal fat mass with adjustment for gestational age and gender. Descriptive statistics, such as mean, median and range will be calculated for all variables. Power and sample size analysis based on our preliminary mitochondrial  $\beta$ -oxidation data in obese women (38±14 nmol/mg/hr) showed that a sample size of N=18/group achieves 80% power to detect a difference of 25% between groups using a two-sample t-test with a significance level of 0.05.

• *Provide a power analysis.* These are included in the statistical analyses.

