# 🗹 Yes 🛛 No

If **Yes**, describe the following:

- *The randomization procedures, including the ratio of subjects randomized to each study arm.* Yes through a computer generated randomization stratified for overweight vs. obese and breastfeeding status.
- *The blinding procedures if the study will be blinded.* N/A, only the statistician analyzing data will be blinded.

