## **10.3** Resources Available

• Specify the role and tasks delegated to each research team member.

Pennington Biomedical Research Center – Research team members will perform analysis of data, and interactions with participants during recruitment, evaluation in the clinical research unit, for nutrition, and for lifestyle changes. Please see addendum for site specific procedures.

Massachusetts General Hospital & Brigham and Women's Hospital-- Potential participants will be recruited from eligible women who have delivered infants at MGH and BWH. TMC study staff will reach out by email, phone, or mail to women who agree to be contacted at a later date and will offer study participation. Consent and all subsequent study procedures will be conducted at Tufts Medical Center or

Brigham & Women's Hospital for those women who elect to participate. Cord blood and placental collection will be done according to standard of care at the respective hospitals. BWH or MGH LIPP research staff will collect designated tissue specimens from the research participant's hospital. Samples will be collected according to protocol, aliquoted and processed as needed and placed on ice or liquid nitrogen. The designated samples will either be transported to TMC/MIRI for further processing and storage by LIPP staff until analysis or processed and stored at BWH until analysis. Neonatal anthropometrics will be performed at the institution by LIPP staff and be used as an alternative measure for body fat if a PeaPod is not available. Neonatal anthropometrics may be conducted at the houses of LIPP participants with their consent if a participant delivers at a facility other than an approved LIPP study site and are unable to travel to BWH, MGH or TMC after delivery. Both anthropometrics and PeaPod will be performed otherwise. Additionally, for those participants who deliver at BWH or MGH, LIPP research staff will conduct study sample collection according to the site protocol. In addition to infant measures and study sample collection, LIPP study staff will conduct maternal questionnaires prior to delivery and post-delivery. Before delivery, the Infant Feeding Intention Scale will be conducted; after delivery, questionnaires will include the Breast-Feeding Self-efficacy after Delivery, Infant Feeding Practices Scale and the Holmes-Rahe Life Stress Inventory.

• At Tufts Medical Center;

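### Aim 2's placental oxidation result appears to rest on a fresh-tissue subset with no selection rule and no masking at collection or assay, yet it is labelled intent-to-treat

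*Combined protocol and SAP*

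**What the plan says.** - **Aim 2 question (section 8.2).** "The primary goal of Aim 2 is to determine the effect of lifestyle intervention prior to pregnancy on placental mitochondrial fatty acid oxidation at term".
- **How it is measured (section 3, Specific Aim 2).** Using isotopes, "labeled fatty acid oxidation and esterification will be quantified in vitro in placental explants".
- **What happens to the placentas (section 5.3, sample handling).** Tissue is fixed for histology, "submerged in RNA Later, or snap frozen in liquid nitrogen and stored at -80°C for molecular analysis". The next sentence is the only one on fresh tissue: "For a subset of the subjects, we will obtain fresh placental tissue for lipid metabolism activity assays".
- **Who collects (section 10.3).** "BWH or MGH LIPP research staff will collect designated tissue specimens from the research participant's hospital". The Pennington addendum (section 11.1) likewise has study staff collect at the delivery hospital.
- **Masking (section 8.5).** "only the statistician analyzing data will be blinded".
- **Analysis (section 8.2).** "We will conduct an intent-to-treat analysis using two sample t-test or non-parametric Wilcoxon rank-sum test to assess differences between groups". The stated sample size is 18 per group, for 80% power to detect a 25% difference given 38±14 nmol/mg/hr.

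The plan does not give the size of the fresh-tissue subset, who chooses it, when or by what rule, whether it is balanced by arm or site, any time limit from delivery to assay, or how women without fresh tissue enter the analysis.

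**The concern.** An intent-to-treat comparison takes its protection from randomisation: everyone allocated is compared as allocated. Here a woman contributes an oxidation value only if she conceives, delivers within the study and is then one of those from whom fresh tissue is taken. The last step is under the study's control and is left undefined. People who may know the arm handle the tissue, and the plan masks neither collection nor assay.

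At stake is the main mechanistic result. A difference in oxidation could reflect which placentas were assayed, or how long they waited, rather than the intervention. The planned regressions of oxidation on maternal cytokines, insulin resistance and neonatal fat mass would inherit the same subset.

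**Working it through.** **1. Does the main measure depend on the subset?** Section 3 says oxidation is measured in explants in vitro. Section 5.3 assigns preserved tissue to histology and molecular analysis, and fresh tissue to lipid-metabolism activity assays. No single sentence says that the explant assay needs fresh tissue; this follows from reading the two sections together. The expression and lipid-content measures on preserved tissue are not confined to the subset.

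**2. How far is the subset from the randomised set?** Section 3 plans 200 women. Section 8.2 expects at least 50 per group after 50% dropout, so about 100 deliveries. If the subset were 18 per group (the plan never says so), it would hold 36 placentas: 36/200 = 18% of those recruited and 36/100 = 36% of those delivering.

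**3. Is 18 per group enough?** Inputs from section 8.2: mean 38; SD 14 (reading the ± figure as an SD); difference 0.25 × 38 = 9.5; alpha 0.05, taken as two-sided; power 80%.

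- Required n per group = 2 × [14 × (1.96 + 0.84)/9.5]² = 2 × 17.05 = 34.1, so 35. The t-based value is 35.1.
- Power at 18 per group: SE = 14 × √(2/18) = 4.67 and 9.5/4.67 = 2.04, giving 53% (normal) or 51% (t).
- Detectable difference at 18 per group with 80% power: 13.1 (normal) to 13.5 (t) nmol/mg/hr, or 34 to 35% of 38.

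Attempts to reproduce 18:

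| Variant | Result |
|---|---|
| One-sided test | 27 per group (t-based 28) |
| 25% taken of the higher mean (38/0.75 − 38 = 12.67) | 20 per group; power at 18 is 77% (normal) or 75% (t) |
| Two-sample factor of 2 left out | 17.05, rounded up to 18 |

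Only the last gives 18 exactly, and it is not a two-sample calculation. With 35 per group, 70 placentas are needed, or 70/100 = 70% of expected deliveries. At the 40% dropout also mentioned in section 8.3, deliveries would be 200 × 0.6 = 120 and the share 70/120 = 58%.

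**4. What could selection do?** The documents give no basis for a bias, so this is an illustration. Suppose there is no true effect, but selection or handling shifts the arm difference by b. By the normal approximation, the two-sided false-positive rate is Φ(−1.96 + b/SE) + Φ(−1.96 − b/SE), with SE = 14 × √(2/n).

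| Assumed shift b | 18 per group | 35 per group |
|---|---|---|
| 0.25 SD (3.5) | 12% | 18% |
| 0.5 SD (7.0) | 32% | 55% |

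The nominal rate is 5%. For the same shift, a larger subset makes the error more likely. Correcting the sample size therefore does not replace a selection rule.

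**The case against.** The strongest reply is that the documents show an omission and no actual bias. No passage says when the subset is chosen, by whom, or what hours the laboratory keeps. That stands. A reader might infer that staff pick women at delivery knowing the arm, or that planned daytime deliveries would fill most of the subset. The documents support neither. The second would also need laboratory hours and the share of planned deliveries, and neither is given.

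A reader might also infer that Pennington placentas yield no fresh assay, since samples are stored there and shipped later. The addendum has tissue taken at once to that centre for processing and refers to an operating procedure that is not reproduced. The plan does not say where the assay is run, so this too is unsupported. That procedure may hold more detail, but for one site only.

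Other points:

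- **Specimens are already coded** (sections 5.3 and 6.4). True, and the fix should build on it. But coding is not a statement that assay staff are masked, and section 8.5 names only the statistician.
- **The 18 per group may be the intended subset size.** Possibly, but the plan never links the two, and a number does not say who is chosen.
- **The intent-to-treat label is used for the Aim 1 comparisons too.** True. Aim 2 adds a further layer of selection that the investigators themselves control.
- **A list cannot stop deliveries being missed.** True. What it gives is a known denominator, so missing tissue can be counted by arm.
- **Resources are short** (sections 5.1 and 5.3). This is a fair reason not to demand fresh tissue at every delivery, and the point does not depend on that.
- **This is a mechanistic aim.** Section 8.1 makes neonatal adiposity the primary outcome and does not list placental oxidation. That limits the severity.

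**Conclusion.** The concern holds in this form: Aim 2's main measure appears to depend on fresh tissue from an undefined subset, nothing prevents selection or handling that depends on arm, and the resulting comparison is not intent-to-treat. It should be corrected, but it does not touch the trial's primary outcome.

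The size of any bias cannot be derived from the documents; the 12% to 32% false-positive rates rest on assumed shifts of 0.25 to 0.5 SD. The sample-size shortfall rests on the plan's own figures, with ±14 read as an SD and the test as two-sided: about 35 per group are needed against 18 stated, with 51 to 53% power at 18. A reader might take 36 placentas as sufficient because section 8.2 states 18 per group; the plan's inputs do not bear that out.

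**What to change.** - **Section 5.3:** state the size of the fresh-tissue subset and select it by a rule set before delivery and without knowledge of arm. Examples are a computer-generated list balanced by arm and site, with collection staff told only whether fresh tissue is wanted, or consecutive deliveries. Log delivery mode and delivery-to-assay time.
- **Section 8.5:** extend the existing specimen coding so that assay staff are masked to arm, and say so.
- **Section 8.2:** describe the oxidation result as a comparison by randomised arm within the fresh-tissue subset. Report fresh-tissue availability by arm, with reasons where it is missing. Correct the sample size to about 35 per group, or state the difference that 18 per group can detect (34 to 35%).

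The selection, masking and labelling changes cost a generated list, two log fields and revised wording. Some selected deliveries will be missed and must be counted as missing, the rule cannot reach placentas already collected, and the oxidation claim becomes narrower. Assaying 35 rather than 18 per group has a real laboratory cost; if that cannot be met, the lower power should be stated.

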# 5.4 Collection and Storage of Human Biological Specimens (Tissue Banking)

Will biological specimens be stored for future, unspecified, research?

Yes, please see Form 6 and attached letter.

x **T** Yes

# 6 Ethics and Protection of Human Subjects

# 6.1 Informed Consent Process

Will subjects be required to provide informed consent?

🗹 Yes 🛛 🗆 No

If **Yes**, describe the following:

• Where the consent process will take place (e.g. a private clinic room.)

Informed consent will take place at the postpartum visit or at the time of the 3-month postpartum metabolic visit before testing.

• Anticipated amount of time a potential subject will have to make a decision about participation in the study.

Three calendar months.

• Processes to ensure ongoing consent throughout the study.

Frequent visits and contacts and the ability to take the consent form home before needing to sign consent at or prior to the baseline visit. In addition to the re-consent process, participants will be asked to provide verbal consent at the beginning of their early pregnancy visit (12-16 weeks gestation). Verbal consent for neonatal measures will also be collected after participants deliver.

• State if you will follow "SOP: Informed Consent Process for Research (HRP-090)". We will follow the SOP: Informed Consent Process for Research (HRP-090)".

- Non-English Speaking Subjects NA
  - Describe the consent procedures that will be used to enroll non-English speakers (for example, the use of IRB approved Short Forms per the IRB's Short Form policy). If IRB approved Short Forms will not be used describe who will conduct the consent interview, use of interpreters, use of IRB approved translated documents, etc.
  - If non-English speakers are being excluded, provide the ethical and scientific justification, including whether this would be equitable. For example, if non-English speakers are eligible for the study and could potentially benefit from participation, it would not be equitable to exclude them.

The study is very detailed and involves 1-2 years of participation in the program. If we are able to hire a research coordinator who is proficient in a language other than English we will consider recruiting non-English speakers. We will consider the use of interpreters for non-English speakers after the study is up and running at TMC/HNRCA and BWH.

*Refer to the IRB Short Form Policy* on the IRB website for information on enrolling non-English speakers.

- Process to Document Consent in Writing
  - State if you will follow "SOP: Written Documentation of Consent (HRP-091)". If not, describe how consent will be documented in writing.
     We will follow the SOP: Written Documentation of Consent (HRP-091)
  - If you will obtain consent, but will not document consent in writing, attach a consent script and confirm the following (you may use Tufts IRB ICF templates to create the consent document or script): NA

